# 3. STUDY DESIGN

The study design is a multi-centre prospective cohort diagnostic accuracy study with 3 year follow-up. Once enrolled into the study, the participants will be monitored following standard clinical practice in the diseased eye. The standard of care in the NHS for patients newly diagnosed with nAMD is regular (approximately every 8 weeks) assessment and treatment if required. At each monitoring visit, patients will be examined using all index tests in the study eye (unaffected) and a reference standard measurement triggered if any of the index tests are positive (see flow chart). All patients will be followed-up according to standard clinical practice until confirmed treatment for nAMD in the study eye or until 3 years from enrolment, whichever is sooner. Patients who do not have confirmed nAMD in the study eye during the follow-up period will have a FFA at 18 months and 3 years. The study has been designed to have minimum impact on the current patient care pathway. A schematic of the study design is shown below.

Individuals screened as potentially eligible nAMD (n = 1667)

- Newly diagnosed
- One eye affected and second eye unaffected (confirmed by FFA at routine standard of care (SOC) visit\*)
- About to commence or recently commenced anti VEGF therapy in affected eye
- Age 50-95

\* Referred to as "diagnostic FFA" from now on

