#### 3.6.6. Follow-up procedures

Once enrolled into the study, the participants will be clinically monitored following standard clinical practice in the eye with nAMD. The standard of care in the NHS for patients newly diagnosed with nAMD is regular (approximately every 8 weeks) assessment and treatment as required. At each follow up clinic visit VA, clinical signs on fundus, comments on the OCT appearance, self reported function and Amsler [index tests that are performed in the EDNA study eye] will be extracted. A FFA (reference standard assessment) will be triggered if any of the index tests are positive (see flow chart). Following this a clinical diagnosis of the presence of nAMD in the study eye will be made. If nAMD is diagnosed the patient will be clinically monitored and treated as per local clinical practice.

At M 18 a study visit which will occur if the participant remains in the study by virtue of not having experienced a neovascular event in the EDNA study eye, all tests undertaken at baseline along with an FFA will be performed with subsequent clinical diagnosis of the presence of nAMD in the study eye. Similarly, at M 36 a study exit visit which will occur if the participant remains in the study by virtue of not having experienced a neovascular event in the EDNA study eye during the entire period of follow up, all the tests recorded at baseline along with an FFA will be performed.

If, as part of routine clinical management, an additional FFA is performed in the non study eye and results in the detection of nAMD in the EDNA study eye then these results should be recorded in the EDNA CRF and study monitoring follow-up will cease.

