# 3.6.8. Change of Status/Withdrawal procedures

Participants will remain in the study unless they choose to withdraw consent or if they are unable to continue for a clinical reason. All changes in status with the exception of complete withdrawal of consent will mean the participant is still followed up for all study outcomes wherever possible. All data collected up to the point of complete withdrawal will be retained and used in the analysis unless the participant requests this to be destroyed and excluded. If the participant had previously consented to and donated blood for storage, and the participant later withdraws consent, they may also request for their donated blood to be destroyed.

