## **Design**

The study design is a multi-centre prospective cohort diagnostic accuracy study with 3 year follow-up. Once enrolled into the study, the participants will be monitored following standard clinical practice in the diseased eye. The standard of care in the NHS for patients newly diagnosed with nAMD is regular (approximately every 8 weeks) assessment and treatment if required. At each monitoring visit, patients will be examined using all index tests in the study eye (unaffected) and a reference standard measurement triggered if any of the index tests are positive. All patients will be followed-up according to standard clinical practice until confirmed treatment for nAMD in the study eye or until 3 years from enrolment, whichever is sooner. Patients who do not have confirmed nAMD in the study eye during the follow-up period will have a FFA at 18 months and exit. The study has been designed to have minimum impact on the current patient care pathway.

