### **Participant inclusion criteria for analysis A**

For each of the 5 index tests, the following criteria will be applied separately:

1. Last FFA result shows no nAMD:

The participant will be included if there is **at least one prior** index test result during the follow-up period.

2. Last FFA result shows nAMD:

The participant will be included if there is an index test result within the previous 3-months. If a participant does not have an index test result within the previous 3-months of their last FFA the FFA will not be considered valid and we will look for an earlier FFA result for the participant and apply rules 1 and 2 again on the earlier FFA.

If no follow-up FFA is available which satisfies either criteria, then the participant will be excluded. If no follow-up FFA is available, the participant will be excluded from the analysis.

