**Missing data and indeterminate and unreliable results**

Absence of a positive reference standard during valid follow-up period will be presumed to indicate a negative result.

Indeterminate FFA results: As a default position indeterminate tests will be treated as missing, but there will be sensitivity analyses to test that assumption (see below). For the primary person level analysis (Analysis A1), if the last available reference standard is missing/indeterminate then the previous reference standard will be used. If no reference standards have been carried out after the baseline reference standard or they are all indeterminate/missing then that participant will be excluded from the analysis unless a curtailed period with a valid FFA and index test result exists.

For the prognostic model (Analysis D) the impact of missing covariate data will be assessed and multiple imputation will be used for baseline variables if considered appropriate.

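### For participants with no scheduled FFA, entry to analysis A1 depends on the index results: those with a false alarm are kept and those negative throughout are dropped

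*SAP*

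**What the plan says.** **Who is excluded.** The SAP, under Participant inclusion criteria for analysis A, states: "If no follow-up FFA is available, the participant will be excluded from the analysis". The missing-data section repeats this for A1: "If no reference standards have been carried out after the baseline reference standard or they are all indeterminate/missing then that participant will be excluded", unless a shorter period with a valid FFA and index result exists. When the last FFA is negative, one earlier index result is enough for inclusion.

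**Where a follow-up FFA comes from.**
- Triggered: the SAP Design section has a "reference standard measurement triggered if any of the index tests are positive".
- Scheduled, whatever the index results: participants without confirmed nAMD "will have a FFA at 18 months and exit" (SAP Design) or "will have a FFA at 18 months and 3 years" (Protocol section 3).
- Incidental: Protocol 3.6.6 asks sites to record the result when "an additional FFA is performed in the non study eye and results in the detection of nAMD in the EDNA study eye".

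**How the same people are treated elsewhere.** Protocol section 8 counts a participant who is negative throughout as a true negative if there is no positive FFA, and states no requirement that an FFA was done. It also says the SAP prevails where the two differ. Analysis B in the SAP takes an absent FFA as negative. Reference definition C, used in A7, accepts an FFA that was not done if the clinical diagnosis is negative. Sensitivity analyses 1 to 6 do not restore the excluded participants to A1.

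**The concern.** Take two people without nAMD who both leave at month 10. One had a false alarm at month 6 and a negative FFA, so she is in A1 as a false positive for the test that fired. The other was negative on everything. She has no FFA and is left out, although she would be a true negative on all five tests. The same split applies to people who stay in monitoring but have neither scheduled FFA.

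For this group, the tests under evaluation decide who enters the table that evaluates them. Every non-converter removed is negative on every test, so each specificity denominator shrinks while the false positives stay. All-negative participants who had converted undetected and have no FFA are lost too, which can push sensitivity up. Sensitivity and specificity are the primary diagnostic outcomes.

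**Working it through.** **The plan's own figures.** The documents give no figure for this effect, so the sample-size statement serves as the anchor.
- Sensitivity: with disagreement 0.30 and difference 0.15, cases = (1.96×√0.30 + 1.2816×√(0.30 − 0.15²))² / 0.15² = 135.9, taken as 136; 136/0.28 = 486, against the stated 491. Then 491/0.88 = 558, against 560.
- Specificity, 94% v 87%: maximum disagreement is 0.06 + 0.13 = 0.19, and (1.96×√0.19 + 1.2816×√(0.19 − 0.07²))² / 0.07² = 403. That equals 560 × 0.72, the expected non-converters. The 7-point planned difference is therefore reproduced.

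**Formula.** A1 specificity = 1 − FP/(n₀ − D), where n₀ is the number of non-converters, FP the false positives, and D the all-negative non-converters with no scheduled FFA.

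**Group 1: leaving before month 18.**
- Early loss is 1 − 0.88^0.5 = 6.2% (12% over 3 years, from the sample-size section) to 1 − 0.9^1.5 = 14.6% (the quoted ceiling of 10% per year, about 27% over 3 years). Of 403 that is 25 to 59 people.
- Assumptions: mean follow-up 9 months, constant false-alarm rates, 87% specificity at 3 years, and 30-50% with a false alarm on any test over 3 years.
- By 9 months, one test has fired falsely in 1 − 0.87^0.25 = 3.4%, and any test in 1 − 0.7^0.25 = 8.5% to 1 − 0.5^0.25 = 15.9%.
- At 6.2% loss: FP = 0.938×0.13 + 0.062×0.034 = 0.124 of n₀. Keeping everyone gives 87.6%. A1 drops 5.2-5.7% of n₀ and gives 86.8-86.9%.
- At 14.6% loss: FP = 0.116. Keeping everyone gives 88.4%. A1 drops 12.3-13.4% and gives 86.6-86.8%.

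A1 is thus 0.7-1.8 points below the figure with all leavers kept, but only 0.1-0.4 points from the assumed 87%. The kept-everyone figure is itself above 87% because it adds people observed for about 9 months.

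A simulation gave the same picture. It used 19 visits, five independent tests, constant non-informative dropout and every positive verified. At 12%, 20% and 27% three-year loss, A1 was lower than keeping everyone by 0.4, 0.6 and 0.8 points (94% specificity) and by 0.7, 1.2 and 1.6 points (87%). Against 3-year completers it differed by 0.0 to +0.3 points.

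**Group 2: monitored at length, no scheduled FFA.** Exposure is full, so nothing offsets the selection. If this group is a share m of non-converters and a share a have any false alarm over 3 years, D/n₀ = m(1 − a). Each paired specificity difference is divided by 1 − D/n₀.

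| m | a | D/n₀ | A1 specificity (true 87%) | Shift | True 7-point difference becomes |
|---|---|---|---|---|---|
| 10% | 50% | 5% | 1 − 0.13/0.95 = 86.3% | −0.7 | 7.4 |
| 10% | 30% | 7% | 1 − 0.13/0.93 = 86.0% | −1.0 | 7.5 |
| 20% | 50% | 10% | 1 − 0.13/0.90 = 85.6% | −1.4 | 7.8 |
| 20% | 30% | 14% | 1 − 0.13/0.86 = 84.9% | −2.1 | 8.1 |

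The shares m are illustrations; the documents give none.

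**McNemar.** The people removed are negative on both tests in every pair. McNemar's statistic uses only discordant pairs, so its p-value does not move. The estimated differences and their Newcombe intervals do.

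**The case against.** Several stronger readings are tempting, and the documents do not support them.

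- *Everyone who withdraws or dies is affected.* No. A participant who had the month-18 FFA and left later stays in A1, even if negative throughout. Under constant dropout that is about half of leavers.
- *Early leaving biases specificity down by up to 1.8 points.* Only against a comparator diluted by short follow-up. Against 3-year specificity the shift is near zero. That does depend on two effects cancelling under non-informative dropout, which the plan cannot guarantee.
- *Comparisons between tests gain false significance.* McNemar p-values are unchanged.
- *The SAP and protocol schedule the last FFA differently.* Protocol 3.6.6 itself calls month 36 a study exit visit, so the SAP's exit can be the same visit.
- *Protocol 3.6.8 is contradicted, since "All data collected up to the point of complete withdrawal will be retained and used in the analysis".* That is a retention rule and does not promise a place in every 2x2 table. Leavers' data can still enter the GEE, Cox and time-to-conversion analyses.

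Two further defences are partial. The SAP presumes a negative result where no positive FFA exists, but only within the valid follow-up period, which itself needs an FFA. Analysis B and definition C do accept absent FFAs, but neither repairs A1, and the inclusion criteria as written still demand an FFA for A7. Finally, a positive test may not always lead to an FFA (Protocol 7.3 monitors this), and incomplete verification would shrink the effect shown here.

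What stands is the dependence on index results, the unexplained departure from the protocol's true-negative rule, and the lack of any A1 analysis that tests it.

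**Conclusion.** The point holds for participants with no scheduled FFA, and its size is modest against the 7-point planned difference. For early leavers the net effect on 3-year specificity is near zero under non-informative dropout. For people monitored at length without a scheduled FFA there is a real downward bias, of the size in the table, and paired specificity differences grow by 5-8% in relative terms if the group is 10% of non-converters and by 11-16% if 20%. These figures rest on 87% specificity, 30-50% with any false alarm and full verification of positives. The upward pressure on sensitivity from unverified missed converters cannot be sized from the documents. This calls for a sensitivity analysis, not a new primary analysis.

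**What to change.** Keep A1 as the main analysis and make three additions to the SAP.

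1. Add an A1 sensitivity analysis that does one of the following:
   - count participants with no follow-up FFA, all index tests negative and no clinical diagnosis of nAMD as reference-negative, which is the protocol section 8 rule; or
   - weight all-negative participants who had a scheduled FFA to stand for those who did not. This also lets converters missed by every test, but found at a scheduled FFA, represent the unverified ones.
2. Report how many participants are in this group and how long each was followed. Early leavers' short exposure raises specificity in the first option, so the result cannot be read without this.
3. State that the FFA requirement in the analysis A inclusion criteria does not apply to A7.

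The cost is one extra analysis and a few sentences. The first option assumes that unverified all-negative participants are disease-free, and the second that they resemble verified ones. Restricting the main specificity table to participants with a scheduled FFA is a possible alternative, but it discards verified negatives and lets converters enter by a route closed to non-converters, so it is not recommended here.

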### **Definition of valid follow-up period**

If a participant is included as defined above, then the valid follow-up period will be from baseline until the date of the last valid FFA (as defined above).

### **Index test result definition for analysis A**

For each index test, multiple test results will be collapsed into a single test result. Any positive test result over the valid follow-up period will be classed as an overall positive result. To be a negative index test result, all index test results must be negative. The classic 2x2 table for assessing diagnostic accuracy with our definitions is provided in Table 2 below.

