# 3.6.7. End of participant follow-up

All patients will be followed-up according to standard clinical practice up to 3 years from enrolment. Study monitoring follow-up will end prior to 3 years upon a clinical diagnosis of nAMD in the study eye or if a patient withdraws consent to continue this follow-up (see section 3.6.8 for information on the withdrawal procedures).

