#### 7. SAMPLE SIZE, PROPOSED RECRUITMENT RATE, MILESTONES & INTERNAL PILOT

#### 7.1 Sample size

The sample size is based upon comparative diagnostic accuracy to ensure the ability to detect differences in sensitivity and specificity between candidate tests. The calculation is based upon McNemar's test. (Obuchowski 1998) Under the primary analysis, a positive candidate test result will be defined as any positive result during the monitoring period on the respective test. At 2-sided 5% significance level and 90% power, a paired difference of 15% (80% to 65%) in sensitivity will require 491 participants (560 allowing for indeterminate/missing data results - including patients lost to follow-up cumulatively of up to 12%) given a cumulative incidence of 28% at 3 years.(Karnon 2008) This calculation assumes a disagreement between tests of 0.30 which was based upon data from a diagnostic study involving OCT for diagnosis glaucoma (HTA reference 09/22/111). A smaller difference in specificity will be identifiable (7%; 94% to 87% with power and significance levels as before) given most participants will not convert during the 3-year follow-up period even if the maximum level of disagreement occurs. The reference sensitivity and specificity values used in this calculation are the values observed for OCT in a pilot study with a similar study design.(Parnick-Silver 2012) Differences in sensitivity and specificity of at least 20% will also be detected at the same power and significance levels even

if the sensitivities/specificity are substantially lower (e.g. 60 to 40%) or the level of missing data is higher (e.g. 20%). These calculations conservatively assume maximum possible disagreement between tests. A sample of this size would be of sufficient size for other measures of diagnostic performance (e.g. the sensitivity and specificity of individual technologies will be estimated to 95% confidence interval of width 16% and 10% respectively given a sensitivity/specificity of 65% or higher). Such a sample will also provide a sufficient sample for the GEE analysis given the anticipated gain in precision due to use of multiple repeated measures over time.(Rochon 1998) Similarly, this sample will be more than sufficient for the development of a risk prediction model with over 130 events (conversions to AMD) anticipated and given 10 events per predictor variable/contract are typically recommended.(Peducci 1995)

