#### 8. STATISTICAL ANALYSIS

Participants are categorised as AMD or not AMD according to the presence of a positive FFA result during the follow-up period. Two main statistical analyses of diagnostic accuracy are planned, a) the primary single test result diagnostic accuracy analysis and b) a more secondary complex analysis which utilises repeated test results.

Under the first approach, repeated monitoring test assessments are collapsed over time to give a single candidate test result (positive or negative). The presence of a positive candidate test result within a fixed time period (e.g. within 6 months of diagnosis/study completion) of the positive reference standard value is treated as a true positive, positives outwith this period are false positives, participants who tested negative through the period are either true negative (if there is no positive reference standard test within the follow-up period) or false negative (if not). Under the primary analysis, monitoring sensitivity and specificity of the tests will be compared using McNemar's statistical test (with 95% confidence intervals produced using Newcombe's method).(Newcombe 1998) Sensitivity analyses will include assessment of alternative definitions of a positive test result in a monitoring setting (e.g. using only the test result at diagnosis/study completion), and consider combinations of tests. Sensitivity, specificity, positive and negative likelihood ratios and (when possible) the area under the receiver operating characteristics curve will be calculated (with 95% confidence intervals) for each test using FFA test results as assessed by the responsible ophthalmologist as the reference standard (Zhou 2002, Altman 2000). A secondary analysis will use an alternative reference standard of FFA test results as assessed by the reading centre. A ROC curve for each imaging test will be produced and the area under the ROC curve will also be formally compared between technologies. (DeLong 1988) All analyses will be conducted at 5% (2 sided) significance level with 95% confidence intervals produced where appropriate.

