# Planned subgroup analyses

We will undertake pre-planned subgroups evaluation according to type of AMD (Classic CNV, Occult CNV, RAP and IPCV). These subgroup analyses will be classified as exploratory and evaluated at the 2-sided 5 significance level.

All study analyses will be according to a statistical analysis plan that will be agreed in advance by the Study Steering Committee. Should the analysis plan deviate from the approved protocol, the analysis plan shall take precedence.

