**Table 2 Two by two table: definitions of test and disease status.**

	Index positive	Index negative
Reference standard positive: nAMD	True positives Any reference standard indicates nAMD in study eye AND Any index test result is positive during valid follow-up period	False negatives Any reference standard indicates nAMD in study eye AND Index test negative for all available prior time points
Reference standard negative: No nAMD	False positives All reference standard results indicate no nAMD in study eye AND Any positive index test result during valid follow-up period	True negatives All reference standard results indicate no nAMD in study eye AND Index test negative for all available prior time points

Sensitivity and specificity will be calculated with 95% confidence intervals calculated using the Agresti-Coull method (Zhou 2002). Positive and negative likelihood ratios will also be calculated with 95% confidence intervals calculated using the method in Zhou 2002. Diagnostic odds ratios and the proportion of indeterminate tests will be calculated with 95% confidence intervals. A ROC curve will be plotted and the area under the ROC curve calculated using the trapezoidal rule for visual acuity tests. The standard error for the AUC will be calculated using the method of DeLong, DeLong and Clarke-Pearson (1998) and used to form an asymptotic normal 95% confidence interval.

Monitoring sensitivity and specificity of the tests will be compared using McNemar's statistical test (with 95% confidence intervals produced using Newcombe's method) (Newcombe 1998).

For comparing sensitivities under the primary analysis, the McNemar 2x2 table will be constructed using only patients who have had a positive FFA result. They will be classified as having a positive index test, if the index test has any positive results during the valid follow-up period. They will be classified as having a negative index test, if all prior available tests have been negative during their valid follow-up period. For comparing specificities under the primary analysis, the McNemar 2x2 table will be constructed using only patients who have had negative FFA results throughout using the same index test classification.

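### Primary analysis A1 credits a test with detecting nAMD for any positive since baseline, including positives already followed by a negative FFA, which favours less specific tests

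*SAP*

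**What the plan says.** The SAP collapses each participant's repeated results into one result per index test: "Any positive test result over the valid follow-up period will be classed as an overall positive result" (Index test result definition for analysis A). The window is long: "the valid follow-up period will be from baseline until the date of the last valid FFA" (Definition of valid follow-up period). In Table 2 a participant with a positive FFA is a true positive if "Any index test result is positive during valid follow-up period". The text below that table applies the same rule to FFA-positive patients in the McNemar comparison of sensitivity: "They will be classified as having a positive index test, if the index test has any positive results during the valid follow-up period". Nothing ties the positive result to the time of conversion, and nothing deals with a positive that an FFA has since contradicted.

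Such positives will occur. A positive index test triggers an FFA (Protocol 3.6.6), and monitoring goes on if that FFA is negative. Apart from withdrawal, the only early end is conversion: "Study monitoring follow-up will end prior to 3 years upon a clinical diagnosis of nAMD in the study eye" (Protocol 3.6.7).

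The protocol gives two rules for the primary analysis. Section 7.1, repeated in the SAP's sample size text, says that "a positive candidate test result will be defined as any positive result during the monitoring period on the respective test". Section 8 credits only positives within a fixed period of the positive FFA, with 6 months as an example, and adds that "positives outwith this period are false positives". Section 8 also settles precedence: "Should the analysis plan deviate from the approved protocol, the analysis plan shall take precedence".

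**The concern.** Take a participant whose Amsler test is positive at month 4, with a negative FFA, and who converts at month 30 with a negative Amsler test. A1 scores this as an Amsler true positive, although the test missed the conversion. A test that raises more false alarms collects more of these credits, so its sensitivity among converters rises because its specificity is poor.

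The trial's main question is which test detects conversion best, and the primary McNemar comparison of sensitivity is built on this classification. The sensitivity estimates are also meant to feed the economic model (Protocol section 9).

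Other parts of the SAP recognise that timing matters. The inclusion criteria for analysis A require an index result within 3 months before a positive FFA, yet the positive that counts may be years older. Sensitivity analysis 4 in Table 4 refers to acuity positives that FFA has shown to be false, and restarts the acuity comparison from there.

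**Working it through.** **Inputs from the documents** (Protocol 7.1 and SAP Sample size): two-sided 5%, 90% power, sensitivities 80% v 65%, disagreement 0.30, cumulative incidence 28%, 491 participants (560 with 12% loss), design specificities 94% and 87%. Visits are about 8-weekly, so 156/8 gives about 19 in three years.

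**Assumptions, not in the documents:** a constant false-positive rate per visit, independence between visits, a constant conversion hazard, disagreement held at 0.30, and alternative three-year specificities of 70% and 50%.

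**1. The plan's own figure.** n = [1.960√0.30 + 1.2816√(0.30 − 0.15²)]² / 0.15² = (1.0735 + 0.6751)² / 0.0225 = 135.9, so 136 converters. Then 136/0.28 = 486 participants, against 491 stated; 491/0.88 = 558, against 560. Since 491 × 0.28 = 137, I use 137 converters, which gives 90% power. The sample size arithmetic is sound, so the issue is the definition.

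**2. Chance of an earlier false alarm.** The per-visit rate is fp = 1 − spec^(1/19). Conversion falls at visit k with weight w_k proportional to (1 − h)^(k−1) × h, where h = 1 − 0.72^(1/19). Then f = Σ w_k [1 − (1 − fp)^(k−1)]. At specificity 94%, 87%, 70% and 50%, f is 2.71%, 5.95%, 14.27% and 25.16%. These are also the sensitivities that A1 would report for a test with no ability to detect conversion.

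**3. Effect on the design contrast.** Apparent sensitivity = S + (1 − S) × f. First test (S = 80%, specificity 94%): 0.80 + 0.20 × 0.0271 = 80.54%. Second test (S = 65%) at 87%: 0.65 + 0.35 × 0.0595 = 67.08%. Power = Φ[(D√137 − 1.960√0.30) / √(0.30 − D²)].

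| Second test's specificity | First test | Second test | Difference D | Power |
|---|---|---|---|---|
| 87% | 80.54% | 67.08% | 13.5 points | 83% |
| 70% | 80.54% | 70.00% | 10.5 points | 62% |
| 50% | 80.54% | 73.81% | 6.7 points | 30% |

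With 20 visits and uniform conversion times instead, the differences are 13.4, 10.3 and 6.3 points and the powers 82%, 60% and 27%.

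**4. Direction.** The apparent difference changes by (1 − S₂)f₂ − (1 − S₁)f₁ in favour of test 2.
- Equal true sensitivity of 65%, first test 94% specific: a spurious difference of 0.35 × (0.0595 − 0.0271) = 1.1 points at 87%, 0.35 × (0.1427 − 0.0271) = 4.0 at 70%, and 0.35 × (0.2516 − 0.0271) = 7.9 at 50%.
- Less specific test also the more sensitive (80% at specificity 70%, v 65% at 94%): (0.80 + 0.20 × 0.1427) − (0.65 + 0.35 × 0.0271) = 82.85% − 65.95% = 16.9 points, wider than the true 15.

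**5. What a 6-month window does.** Counting only three earlier 8-weekly visits plus the conversion visit, f falls to 0.85%, 1.9%, 4.8% and 9.1%. The first test then shows 80.2%, and the second 65.7%, 66.7% or 68.2% at specificity 87%, 70% or 50%. The differences are 14.5, 13.5 and 12.0 points. Requiring the positive to follow the latest negative FFA would also remove those remaining earlier positives that had a negative FFA.

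**The case against.** The strongest reply is that A1 is no departure from the protocol. Section 7.1 defines the primary analysis by any positive during monitoring, the SAP repeats it, and the SAP has precedence. This stands: the protocol contradicts itself, and section 8 offers 6 months only as an example. It settles which rule will run, but not whether that rule measures detection.

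The second reply is that the SAP already contains time-linked analyses. A2 ignores positives outside the last 6 months, so for sensitivity it applies section 8's true-positive rule. A3 uses only the visit at which nAMD was diagnosed and would score the Amsler example as a false negative. A5 and A6 do the same against the reading-centre FFA. All four include McNemar comparisons. Analysis B, as I read it, treats the reference as negative until the positive finding, so earlier positives count against specificity. This also stands, and it rules out any claim that the problem is unaddressed. But all of these are secondary, A2 can still count a positive contradicted within the last 6 months, and sensitivity analysis 4 restarts visual acuity only.

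Third, poor specificity remains visible among non-converters. That is true, but it does not repair the comparison of sensitivities.

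Fourth, not every earlier positive has been refuted. After one negative triggered FFA, further FFAs for acuity loss are at the clinician's discretion (Protocol 3.2.3), and the internal pilot anticipates FFAs not being requested after a positive (7.3). The SAP also provides for clinically diagnosed nAMD with a negative local FFA, so some of these positives may be early disease. By the study's own primary reference standard, however, they are false.

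**Conclusion.** The concern holds. As written, A1 counts contradicted positives as detections, raises apparent sensitivity by (1 − S) × f, and favours less specific tests in the primary comparison. The mechanism and its direction follow from the SAP's definitions; the size does not.

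At the documents' own specificities the effect is modest: about 13.5 points observed instead of 15, with power of 82–83% instead of 90%. A reader might infer that power falls to 60% or below 30%. That needs three-year specificities of 70% or 50%, which appear nowhere in the documents, together with the visit, independence and disagreement assumptions above. Such values are not far-fetched under an any-positive rule: an assumed 2% false-positive rate per independent visit gives 0.98^19 = 68%. Even so, they remain assumptions. If false alarms come mostly before conversion, f can approach 1 − specificity, which is 13 points at 87% for a test with no true sensitivity.

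A reader might also infer that the bias always runs toward no difference. It does so only when the more specific test is also the more sensitive; otherwise it can create a difference or widen one.

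The point merits correction before analysis because it determines the headline sensitivities, the documents conflict on it, and the remedy uses data already collected.

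**What to change.** Reconcile Protocol sections 7.1 and 8 with the SAP's sample size text and its index test definition for analysis A. Then:

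- For the primary sensitivity estimates and the McNemar comparison of sensitivity, count a converter as index-positive only if a positive result falls after the most recent negative local FFA and within a stated window before the positive FFA (for example 6 months, as in Protocol section 8 and A2).
- State how specificity is defined. Any positive in a non-converter can remain a false positive, in line with Protocol section 8.
- Compute likelihood ratios and diagnostic odds ratios under one consistent, labelled index-test definition, for example that of A2 or A3, so that they do not mix one rule for sensitivity with another for specificity.
- State whether visual acuity keeps baseline as its reference after a negative FFA. A persistent drop from baseline stays positive at later visits, and the date condition alone does not remove it.
- Keep the present A1 as a labelled secondary analysis.

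The cost is SAP wording and a date condition in the code. Reported sensitivities will be somewhat lower. No new data are needed.
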